### 5.2 Inclusion Criteria

Subjects are eligible to be included in the study only if all the following criteria apply:

1. The subject or legally authorized representative give signed informed consent which includes compliance with the requirements and restrictions listed in the ICF and in this protocol.
2. Understand and agree to comply with planned study procedures.
3. Male and non-pregnant female subjects with age  $\geq 18$  years of age at the time of randomization.
4. Are currently not hospitalized.
5. Have one or more COVID-19-related symptoms within 5 days of symptoms onset ((FDA COVID-19-Related symptom guidance, See Appendix 2, available at: <https://www.fda.gov/media/142143/download>)
6. Must have first positive SARS-CoV-2 viral infection determination (has laboratory-confirmed SARS-CoV-2 infection as determined by PCR, or other commercial or public health assay in any specimen)  $\leq 3$  days prior to start of the first dose.
7. Women of child-bearing potential, defined as all women physiologically capable of becoming pregnant, unless they are using highly effective contraception, as shown below, throughout the study and for 3 months after stopping GT0918 treatment. Highly effective contraception methods include:
  - Total Abstinence (when this is in line with the preferred and usual lifestyle of the patient. Periodic abstinence (e.g. calendar, ovulation, symptothermal, post-ovulation methods) and withdrawal are not acceptable methods of contraception, or
  - Use of one of the following combinations (a+b or a+c or b+c):
    - a: Use of oral, injected or implanted hormonal methods of contraception or other forms of hormonal contraception that have comparable efficacy (failure rate  $< 1\%$ ), for example hormone vaginal ring or transdermal hormone contraception.
    - b: Placement of an intrauterine device (IUD) or intrauterine system (IUS);
    - c: Barrier methods of contraception: Condom or Occlusive cap (diaphragm or cervical/vault caps) with spermicidal foam/gel/film/cream/vaginal suppository;

- Female sterilization (have had prior surgical bilateral oophorectomy with or without hysterectomy) or tubal ligation at least six weeks before taking study treatment. In case of oophorectomy alone, only when the reproductive status of the woman has been confirmed by follow-up hormone level assessment;

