## Appendix 2. Common COVID-19-Related Symptoms

Example of an Assessment of 14 Common COVID-19-Related Symptoms: Items and Response Options

Example items

For items 1–10, sample item wording could be: “What was the severity of your [insert symptom] at its worst over the last 24 hours?”

1. Stuffy or runny nose	None = 0
2. Sore throat	Mild = 1
3. Shortness of breath (difficulty breathing)	Moderate = 2
4. Cough	Severe = 3
5. Low energy or tiredness	
6. Muscle or body aches	
7. Headache	
8. Chills or shivering	
9. Feeling hot or feverish	
10. Nausea (feeling like you wanted to throw up)	
11. How many times did you vomit (throw up) in the last 24 hours? *	I did not vomit at all = 0 1–2 times = 1 3–4 times = 2 5 or more times = 3
12. How many times did you have diarrhea (loose or watery stools) in the last 24 hours? *	I did not have diarrhea at all = 0 1–2 times = 1 3–4 times = 2 5 or more times = 3
13. Rate your sense of smell in the last 24 hours	My sense of smell is THE SAME AS usual = 0 My sense of smell is LESS THAN usual = 1 I have NO sense of smell = 2

14. Rate your sense of taste in the last 24 hours

My sense of taste is THE SAME  
AS usual = 0  
My sense of taste is LESS  
THAN usual = 1  
I have NO sense of taste = 2

\*Assessing COVID-19-Related Symptoms in Outpatient Adult and Adolescent Subjects in Clinical Trials of Drugs and Biological Products for COVID-19 Prevention or Treatment  
Guidance for Industry

\*\* The response options shown for items 11 and 12 are intended only for use with a 24-hour recall period.

Reference to Appendix 5, each symptom will be scored daily by the subject as experienced during the past 24 hours. Also, subject will record the change of overall health and clinical outcomes as below.

- In the past 24 hours, have you returned to your usual health (before your COVID-19 illness)? Yes or No
- In the past 24 hours, have you returned to your usual activities (before your COVID-19 illness)? Yes or No
- In the past 24 hours, what was the severity of your overall COVID-19-related symptoms at their worst? None, Mild, Moderate, or Severe
- In the past 24 hours, have you been hospitalized? Yes, No
- In the past 24 hours, have you required home oxygen? Yes, No
- In the past 24 hours, have you had any limitation on activities? Yes, No

---

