
All hospitalization events and COVID-19 related medical attended visits will be listed.

Time to Hospitalization

Time to Hospitalization (in days) is defined as:

First hospital admission date - first dosing date + 1.

Note: Hospitalization (≥ 24 hours) includes Hospitalization, Emergency room and ICU. Extended Care Facility Admittance is excluded.

The following two summaries will be generated separately:

- All-Cause Hospitalization
- COVID-19 Related Hospitalization

If a patient has not experienced hospitalization by completion or early discontinuation of study/study treatment, the patient will be censored at the date of their last visit during the post-treatment period.

Time to hospitalization will be evaluated up to Day 28 and will be summarized and plotted by treatment group with mITT set using the Kaplan-Meier (KM) method. The 2-sided 95% CIs for the 25th, 50th and 75th percentiles, as well as at days 3, 7, 14 and 28 using the Brookmeyer and Crowley method will be reported when estimable. P-value will be obtained from the log-rank test stratified by age, and sex, race and ethnicity, and number of risk factors at randomization. Hazard ratios and corresponding 95% confidence intervals will be obtained from a Cox proportional hazard model which treated treatment group as a unique covariate, and age, and sex, race and ethnicity, and number of risk factors as stratas. The Cox proportional hazard model will be also performed by subgroup of duration since symptom onset to randomization category (≤ 3 days; > 3 days).

If cases of hospitalization are too sparse (e.g., < 1 case in one treatment group), no time to hospitalization analyses will be performed.

Proportion of Symptom Resolution

All symptom resolution is defined as

all symptoms (those scored 0-3*) on the symptom questionnaire scored as absent (scored 0), with each symptom resolution absent for at least 48 hours.

Note: * Seven individual questions from COVID-19-Related Symptom Questionnaire are included here: questions 3, 4, 5, 6, 7, 8 and 9.

Additionally, all symptom resolution will be defined differently to include all individual questions scored 0-3 and related outputs will be noted as sensitivity analysis. It is defined as

all symptoms (those scored 0-3*) on the symptom questionnaire scored as absent (scored 0), with each symptom resolution absent for at least 48 hours.

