Note: * Nine individual questions from COVID-19-Related Symptom Questionnaire are included here: questions 1 through 9.

The proportion of subjects with all symptom resolution will be performed at Days 3, 7, 14, and 28 by treatment in frequency tables and listed using mITT set. Generalized estimating equation (GEE) model will be fitted with the response of symptom resolution mapped to categories of Yes or No and with treatment, age, stratification factors (sex, race and ethnicity, and number of risk factors), time

effect and time*treatment interaction terms included in the model as covariates. Odds ratios with 95% confidence intervals and p-values will be present.

Total symptom score (seven individual questions from COVID-19-Related Symptom Questionnaire included here are questions 3, 4, 5, 6, 7, 8 and 9) and change from baseline in total symptom score to Days 3, 7, 11, 14 and 28 will be summarized by treatment group. Change from baseline will be compared using mixed model repeated measures (MMRM) with the fixed effects of baseline total symptom score, age and stratification factors (sex, race and ethnicity, and number of risk factors) and the random effect of subjects and with time effect and time*treatment interaction terms included in the model. Change from baseline in total symptom score will also be graphically displayed.

Additionally, total symptom score will be calculated differently to include nine individual questions (1 through 9) and related outputs will be noted as sensitivity analysis.

A summary of overall COVID-19 related symptoms, including overall symptoms severity, overall general physical health and returned to usual physical health, at Days 3, 7, 11, 14 and 28 will be provided in frequency table and listed.

Additionally, the proportion of subjects with at least 2 points decrease in symptom score (total of ratings) from baseline to Days 3, 7, 14 and 28 will be summarized and listed as well. Generalized estimating equation (GEE) model will be fitted with the response of at least 2 points decrease mapped to categories of Yes or No and with treatment, age, stratification factors (sex, race and ethnicity, and number of risk factors), time effect and time*treatment interaction terms included in the model as covariates. Odds ratios with 95% confidence intervals and p-values will be present.

Time to All Symptom Resolution

Time to all symptom resolution (in days) is defined as:

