First date when all symptom resolution status is changed to 'Yes' - first dosing date + 1.

If a patient has not experienced symptom resolution by completion or early discontinuation of study/study treatment, the patient will be censored at the date of their last visit during the post-treatment period.

Time to all symptom resolution will be applying the same KM methods and Cox proportional hazard models introduced in the time to hospitalization section.

Symptom Improvement

Symptom improvement is defined as a change in severity of overall symptoms * from a higher score to a lower score, which is defined as following:

symptoms scored as moderate or severe at baseline are scored as mild or absent,
OR

symptoms scored as mild or absent at baseline are scored as absent.

Note: * The overall symptoms question (overall question 1) under overall COVID-19 related symptoms from COVID-19-Related Symptom Questionnaire is included here.

Additionally, symptom improvement will be defined by individual symptom questions from symptom questionnaire as below and related outputs will be noted as sensitivity analysis. It is defined as a patient experiencing both:

symptoms * scored as moderate or severe at baseline are subsequently scored as mild or absent,

AND

symptoms * scored as mild or absent at baseline are subsequently scored as absent.

Note: * Seven individual questions from COVID-19-Related Symptom Questionnaire are included here: questions 3, 4, 5, 6, 7, 8 and 9.

The proportion of subjects with symptom improvement at Days 3, 7, 11, 14 and 28 will be summarized by treatment in frequency tables and listed using mITT set. Generalized estimating equation (GEE) model is fitted with the response of symptom improvement mapped to categories of Yes or No and with treatment, age, stratification factors (sex, race and ethnicity, and number of risk factors), time effect and time*treatment interaction terms included in the model as covariates. Odds ratios with 95% confidence intervals and p-values will be present.

Time to Symptom Improvement

Time to symptom improvement (in days) is defined as:

Date when symptom improvement status is changed to 'Yes' - first dosing date + 1.

If a patient has not experienced symptom improvement by completion or early discontinuation of study/study treatment, the patient will be censored at the date of their last visit during the post-treatment period.

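### Symptom resolution counts subjects who never had a scored symptom as recovered, because entry accepts 14 symptoms and the endpoint scores seven; related responder definitions also lack a baseline condition

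*SAP*

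**What the plan says.** **Entry.** Protocol 5.2, criterion 5, asks that subjects "Have one or more COVID-19-related symptoms within 5 days of symptoms onset" and refers to Appendix 2, which is headed "Example of an Assessment of 14 Common COVID-19-Related Symptoms: Items and Response Options". There is no minimum severity, and the qualifying symptom need not be one that the endpoints score.

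**Resolution.** SAP 4.10.3 defines all-symptom resolution as "all symptoms (those scored 0-3*) on the symptom questionnaire scored as absent (scored 0), with each symptom resolution absent for at least 48 hours". The note to the main definition limits the items: "Seven individual questions from COVID-19-Related Symptom Questionnaire are included here: questions 3, 4, 5, 6, 7, 8 and 9". A sensitivity version widens them: "Nine individual questions from COVID-19-Related Symptom Questionnaire are included here: questions 1 through 9". Results are given "by treatment in frequency tables and listed using mITT set", and SAP 4.5 defines mITT by randomization and one dose. Time to resolution is dated from the day the status turns to yes.

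**Improvement.** The main definition in SAP 4.10.3 uses overall question 1. Its lead-in requires a move to a lower score. Its second limb reads "symptoms scored as mild or absent at baseline are scored as absent"; Protocol 10.5.2.5 has the same limb. A sensitivity version applies two similar limbs to questions 3 to 9 and joins them with AND.

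**Two-point decrease.** SAP 4.10.3 also summarizes and models "the proportion of subjects with at least 2 points decrease in symptom score (total of ratings) from baseline to Days 3, 7, 14 and 28". The SAP's total symptom score, defined shortly before, covers questions 3 to 9.

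**The concern.** Half of the entry list is invisible to main resolution. A subject who enters with only sore throat and loss of taste scores zero on all seven items at baseline. If those zeros persist for 48 hours the subject is resolved by Day 3, possibly still ill, with nothing having changed. In the time-to-event analysis the same subject may be an event at the very start of the curve. The SAP does not say whether a subject at zero from baseline is an early event, never changes status, or is left out, so the programmer would have to choose.

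At stake is the meaning of a recovery endpoint. Subjects with nothing scored to recover from raise the resolution rate in both arms, shorten the apparent time to resolution and pull the arms together. In the two-point-decrease analysis the same kind of subject works the other way, as someone who cannot respond. These analyses carry odds ratios or hazard ratios with p-values, so they will be read as evidence on symptom benefit.

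**Working it through.** The plan states no figure on this point, so there is nothing to reproduce. The check compares the lists, applies each definition to one subject, and then sizes the effect under stated assumptions.

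**1. Lists.**

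| List | Items | Entry items left out |
|---|---|---|
| Entry (Appendix 2) | 1–14 | none |
| Main resolution | 3–9 | 1, 2, 10–14: runny nose, sore throat, nausea, vomiting, diarrhea, smell, taste |
| Sensitivity resolution | 1–9 | 10–14 |

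The sensitivity analysis narrows the gap but does not close it. The SAP describes it as covering every question scored 0–3, yet questions 10 to 12 are also scored 0–3 and are absent from it.

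**2. A subject with all seven items at zero before dosing, who stays there.**

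- *Resolution:* yes, once the zeros last 48 hours.
- *Main improvement:* not decided by the seven items. A subject with only a runny nose can answer mild on overall question 1 and must then fall to no symptoms. The flaw here is separate: a subject who answers no symptoms both times meets the second limb but not the lead-in.
- *Seven-item improvement:* undecided. If a limb with no qualifying item counts as met, the subject is a responder. Read literally, the subject never experiences the first limb and is a non-responder. The literal reading would also fail a subject with only mild items who recovers fully.
- *Two-point decrease:* on the seven-item total, a baseline of 0 or 1 cannot fall by 2. With g the share of such subjects and r the rate among the rest, the reported rate is (1 − g)r.

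**3. Size for resolution.** Let f be the share with no scored item at baseline and p the true rate among the others. If every such subject stays at zero,

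reported rate = f + (1 − f)p, and reported difference = (1 − f)(p₁ − p₀).

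Both f and p are assumptions. Subjects per arm are f × 334, with 334 = 668/2.

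| f | Per arm | Rates, true 50% vs 62% | Difference (points) | OR | Rates, true 5% vs 8% | Difference (points) | OR |
|---|---|---|---|---|---|---|---|
| 0 | 0 | 50.0 vs 62.0 | 12.0 | 1.63 | 5.0 vs 8.0 | 3.0 | 1.65 |
| 2% | 7 | 51.0 vs 62.8 | 11.8 | 1.62 | 6.9 vs 9.8 | 2.94 | 1.47 |
| 5% | 17 | 52.5 vs 63.9 | 11.4 | 1.60 | 9.75 vs 12.6 | 2.85 | 1.33 |
| 10% | 33 | 55.0 vs 65.8 | 10.8 | 1.57 | 14.5 vs 17.2 | 2.7 | 1.22 |

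Example: 0.10 + 0.90 × 0.05 = 0.145 and 0.10 + 0.90 × 0.08 = 0.172, so OR = (0.172/0.828)/(0.145/0.855) = 1.22.

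**4. If some of them later develop a scored symptom.** Suppose only half stay at zero, equally in both arms, with f = 10%. The low-rate case gives 0.05 + 0.045 = 0.095 and 0.05 + 0.072 = 0.122, OR 1.32. The other case gives 0.50 and 0.608, OR 1.55. The difference still shrinks by (1 − f); it shrinks less if the drug also keeps these subjects free of new symptoms.

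**5. Chance imbalance.** The standard deviation of the between-arm difference in f is √(2f(1 − f)/334): 1.7 points at f = 5% and 2.3 points at f = 10%. In one trial this can push either way.

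**The case against.** The strongest reply is that these are secondary endpoints, that the SAP's multiplicity section (4.10.1.2) covers only the interim analysis, and that dilution under randomization does not produce a false positive in expectation. The nine-item sensitivity analysis picks up runny nose and sore throat. The change in total score is modelled with baseline total as a fixed effect and creates no automatic responders. Neither f nor the resolution rates are in the documents. All of this stands, and it limits the severity. It does not remove the defect, because items 10 to 14 stay outside both resolution lists and no baseline condition is stated anywhere.

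A reader might go further and infer any of the following, which the documents do not support:

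- *That these subjects are certain successes.* They are not: one who later develops cough, fever or fatigue fails resolution, so they carry some information on progression.
- *That the list mismatch also inflates main improvement.* That endpoint is scored on overall question 1. Its conflict over absent-to-absent matters only for subjects who report no symptoms overall at baseline, although entry requires a symptom.
- *That the seven-item improvement version gives automatic success.* That depends on how its AND is read.
- *That most placebo resolution at Day 3 would be spurious.* With an assumed true rate of 5%, the share is 5/9.75 = 51% at f = 5% and 10/14.5 = 69% at f = 10%, but only 2/6.9 = 29% at f = 2%. It follows from the chosen rates.

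**Conclusion.** The point holds for symptom resolution and time to resolution: the SAP as written counts some non-changes as recoveries. The expected effect is an overstated resolution rate, an understated time to resolution, and a risk difference reduced by up to the factor (1 − f). At an assumed f of 2–10% that loss is 2–10% of the difference. On the odds-ratio scale it is small when true rates are mid-range (1.63 to 1.57 at f = 10%) and large when they are low, as they may be at Day 3 (1.65 to 1.22). The reported rates behind these figures, and the 1.22, are limits that assume every such subject stays at zero.

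Main improvement has a separate wording contradiction. Seven-item improvement has an unstated rule. The two-point-decrease analysis includes subjects who cannot respond, if its total is the seven-item score, which is the likely reading but is not stated. Severity is minor to moderate: the primary endpoint is untouched, and f can be counted only from baseline data.

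**What to change.** In SAP 4.10.3:

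1. **Resolution and time to resolution.** Analyse mITT subjects with at least one question in the relevant list (3–9 main, 1–9 sensitivity) scored 1 or more at baseline. Keep the full mITT version as supportive. Report the number excluded per arm.
2. **Main improvement.** Change the second limb to mild at baseline and absent later, and restrict to subjects with overall question 1 at least mild at baseline. Align Protocol 10.5.2.5 or record the departure.
3. **Seven-item improvement.** Restrict to at least one of questions 3–9 scored 1 or more at baseline, and state that a limb with no qualifying item at baseline counts as met.
4. **Two-point decrease.** State which total is used, and restrict to baseline totals of 2 or more.

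Use the baseline in SAP 4.2 and say how a missing baseline questionnaire is handled. SAP 4.2 lets a Day 1 record serve as baseline for subjects screened and dosed on the same day; confirm that it reflects status before the dose, so that the restriction keeps the randomized comparison.

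The cost is SAP wording and slightly smaller denominators, about 33 of 334 per arm if f is 10%. The change corrects what is estimated; it need not raise power.

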4.11 Safety Evaluation

All safety analyses will be based upon the Safety set. All listings and tables will be presented by treatment group.

The overall observation period will be divided into 5 segments:

1. pre-treatment period: from day of patient's informed consent to the day before first dose of study medication
2. on-treatment period: from the day of first dose of study drug (D1) to the day of last dose (up to D14).
3. post-treatment period: from the day after last dose (up to D15) to D28.
4. treatment and post-treatment period: from D1 to D28.
5. safety follow up period: from D29 to D42.

4.11.1 Extent of Exposure

Duration of study treatment exposure, the actual cumulative dose (mg), dose intensity (DI) and relative dose intensity (RDI) will be summarized by treatment.

Duration of treatment exposure is defined as the time from initial dose to last non-zero dose. Duration of treatment is calculated as: (Last Dose Date - First Dose Date) + 1.

Dose intensity is computed as the ratio of actual dose received to actual duration.

Relative dose intensity is computed as the ratio of the dose intensity to planned dose received/planned duration.

In addition, the duration of exposure to study treatment will be categorized into time intervals (0-4 days, 0-7 days and 0-14 days); frequency counts and percentages will be presented for the number of patients in each interval. The number of patients, who have dose reductions or interruptions, and the reasons, will be summarized by treatment.

Listings of all doses of the study treatment along with dose change reasons will be produced.

The safety population will be used for all summaries and listings of study treatment.

The actual dose and duration of GT0918, as well as dose intensity and the relative dose intensity, will be listed and summarized using descriptive statistics. The total daily doses of GT0918 for each patient will be summarized using descriptive statistics (e.g., mean, median, and mode).

4.11.2 Adverse Events

Adverse events will be coded using the Medical Dictionary for Regulatory Activities (MedDRA) Version 24.0 or higher.

An AE is defined as the appearance of (or worsening of any pre-existing) undesirable sign(s), symptom(s), or medical condition(s) that occur after subject's signed informed consent has been obtained.

Treatment-emergent AEs (TEAE) are defined as AEs that either start or worsen in severity on or after the date/time of study drug administration and through the end of study.

Overview of AEs

An overall summary table of AEs will be provided with the number and percentage of subjects (incidence) reporting an event for the following categories:

- All AEs
- All TEAEs
 - TEAEs Related to Study Drug
 - TEAEs with Toxicity Grade 3 and Higher
 - TEAEs Related to Study Drug with Toxicity Grade 3 and Higher
 - Note: Related is defined as "Definitely", "Probably", "Possibly" related, or missing relationship to study treatment.
 - TEAEs Leading to Study Drug Discontinuation
 - TEAEs of Special Interest
- TEAEs by Maximum Toxicity Grade (based on the Division of AIDS (DAIDS) [2])
 - Grade 1
 - Grade 2
 - Grade 3
 - Grade 4
 - Grade 5
 - Not Graded
- TEAEs by Maximum Severity
 - Mild
 - Moderate

- Severe or Medically Significant
- Life Threatening
- Died
- All Serious AEs (SAEs)
 - SAEs Related to Study Drug
 - SAEs with Outcome Fatal

TEAE Summaries by System Organ Class and Preferred Term

The incidence for the following will be summarized by SOC and PT, unless otherwise specify:

- All TEAEs
- TEAEs Related to Study Drug
- TEAEs with Toxicity Grade 3 and Higher
- TEAEs Related to Study Drug with Toxicity Grade 3 and Higher
- TEAEs by Maximum Toxicity Grade
- TEAEs Related to Study Drug by Maximum Toxicity Grade
- TEAEs by Maximum Severity

Adverse event summaries will be ordered by decreasing incidence for SOC, and PT within SOC, in the GT0918 treatment group. In case of equal number of subjects sorting will be done alphabetically.

For each subject and each adverse event, the worst toxicity recorded will be attributed and used in the by-maximum-toxicity summaries.

Separate tables for on-treatment period and safety follow up period will be provided, and below by-subject listings will be provided:

- All AEs
- All AEs Related to Study Drug
- All AEs with Toxicity Grade 3 and Higher

